# 7.2. Multicenter Studies

This study will be conducted by multiple investigators in multiple countries. The participants will be randomized to one of the 5 groups (refer to Table B: in section 3.1) which will be performed in a 2:2:2:1:1 ratio prior to intervention to provide approximately 200 enrolled participants per each MMRVNS group and 100 enrolled participants per each MMRV group (MMRV Lot 1 and MMRV lot 2).

# 7.3. Missing Data

Missing data (missing, incomplete or partial dates, AE measurement [including missing AE severity and relationship], prior and concomitant medications and death date) will be handled as per APPENDIX 2 of this

Analysis Plan Page 33 of 57

analysis plan.

Missing immunogenicity data will not be imputed. Concentration below assay cut-off (i.e., lower limit of quantification or < LLOQ) will be replaced by half the assay cut-off (LLOQ/2) for the purpose of GMC computation.

# 7.4. Examination of Subgroups

No subgroup analyses will be performed for this study. Some analysis will be repeated by country, further details will be included in the relevant sections.

# 8. OUTPUT PRESENTATIONS

Appendix 1 shows conventions for presentation of data in outputs.

The templates provided with this SAP describe the presentations for this study and therefore the format and content of the summary tables, figures, and listings to be provided by IQVIA Biostatistics. Statistical output numbering will follow 'ICH E3 Structure and Content of Clinical Study Reports'.

### 9. DISPOSITION AND WITHDRAWALS

All participants who are enrolled in the study (those who received a study intervention, had a blood draw before study intervention administration, or were randomized), i.e., those accounted for in the ENR, will be accounted for in this study.

Analysis Plan Page 34 of 57

# 9.1. Disposition

Participant disposition, withdrawals, and reasons for exclusion from each analysis set, including inclusion as well as exclusion criteria will be presented for the ENR. Specifically, the number of participants, vaccinated, completed the study, discontinued from the study and the reason for discontinuation will be summarized by study intervention for the ENR. Additionally, the number of participants returning for each visit for the ES will be presented. A summary of the number of participants that discontinued from the study due to Coronavirus Disease 2019 (COVID-19) will be presented.

A listing of the disposition for all participants with early withdrawal or discontinuation due to having COVID-19 related issues information will be provided.

#### 9.2. Protocol Deviations

Protocol deviations (PDs) will be collected in a PD log, as detailed in the Protocol Deviations Management Plan (PDMP). All PDs will be assessed as either important or non-important. PDs will be reviewed by the sponsor, and their status confirmed by the time that all data are cleaned for the Final Analysis. A summary table presenting the number and percentage of participants with important PDs (i.e., those PDs associated to elimination from PPS) will be presented for participants in the ES. A listing of all PDs including an indicator of those excluded from the PPS and an indicator of COVID-19 causality will be provided.

## 9.2.1. Protocol Deviations Related To Study Conduct

A PD is any non-compliance with the clinical trial protocol, GCP, or protocol deviation guidelines requirements.

The non-compliance may be either on the part of the participant, the site principal investigator (PI), the study site staff or the sponsor.

Analysis Plan Page 35 of 57

#### 9.2.2. Protocol Deviations Related To Immunogenicity Analysis

Changes to the procedures or events, which may impact the quality of the immunogenicity data, will be considered significant PDs and will be described within the CSR. This includes any circumstances that could alter the evaluation of the immunogenicity results such as sample processing errors that lead to inaccurate immunogenicity results, and/or inaccurate dosing which could exclude them from the PPS. In addition, participants may also be eliminated from the PPS based on usage of certain concomitant medications or vaccines as described in Section 5.2.2 of the Protocol.

# 10. DEMOGRAPHIC AND OTHER BASELINE CHARACTERISTICS

Demographic data and other baseline characteristics will be presented for ES and PPS. The following demographic and other baseline characteristics will be reported for this study:

- Age (years) at the time of study intervention
- Sex
- Race (as per Clinical Data Interchange Standards Consortium [CDISC] categories)
- Ethnicity

Descriptive statistics (mean, median, standard deviation and range) will be presented for continuous variables and frequency counts and percentages for categorical variables.

Age category (preterm newborn infants (gestational age < 37 weeks), newborn (0-27 days), infant and toddlers (28 days – 23 months), children (2-11 years), adolescents (12-17 years), adults (18-64 years), 65-84 years and >=85 years) will be summarized by study intervention for ES.

Analysis Plan Page 36 of 57

The number of participants enrolled at each country will be summarized by study intervention.

No statistical testing will be carried out for demographic or other baseline characteristics.

# 11. GENERAL MEDICAL/VACCINATION HISTORY AND EXAMINATIONS

Medical/Vaccination History information will be summarized for the ENR.

[figure not shown]
- Medical History will be coded using Medical Dictionary for Regulatory Activities (MedDRA) central coding dictionary, Version 27.0 or higher.
- Data captured on the "Medical History" page of the eCRF will be presented by System Organ Class (SOC) and Preferred Term (PT). Medical occurrences that begin before the start of study intervention but after obtaining informed consent will be recorded on the Medical History section of the eCRF, not the AE section.
- Vaccine history will be checked for each participant with the participant's parent/LAR.

A listing of medical/vaccination history data will be provided.

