Recording of solicited administration site events (Days 1–4 post dosing)	0	0				Only events at the MMRVNS vaccine or MMRV vaccine administration site will be solicited
Recording of solicited systemic events (drowsiness and loss of appetite) (Days 1-4 post dosing)	0	0				See Section 8.3 for details and Appendix 3 for definitions
Safety follow-up with clinical staff to review post-vaccination safety data			•			
Recording of solicited systemic events (fever, measles/rubella-like rash, varicella-like rash and other rash [not measles/rubella-like rash or varicella-like rash]) (Days 1–43 post dosing)	0	0	0	0		See Section 8.3 for details and Appendix 3 for definitions
Recording of nonserious AEs (Days 1–43 post dosing)	•	•	•	•		See Section 8.3 for details and Appendix 3 for definitions
eDiary/app completion reminder		•				

Age	4 to 6 years of age at the time of study intervention administration					Notes
Type of contact	Visit 1	Safety call	Visit 2 [†]	Visit 3	EoS	
					Safety follow- up contact	
Timepoints	Day 1	Day 2-3	Day 15	Day 43	Day 181	
Review of eDiaries/app data		0	•	•		The study center staff should review that parent/LAR captured the info in the eDiaries/app before the eDiaries are returned or app uninstalled
Return of eDiaries/uninstall or disable the app				0		
Recording of SAEs	•	•	•	•	•	See Section 8.3 for details and Appendix 3 for definitions
Recording of SAEs related to study participation, or to a concurrent GSK medication/vaccine	•	•	•	•	•	The collection and reporting periods start once the participants' parent(s)/LAR(s) informed consent is obtained
Study conclusion					•	See Section 4.5 for the definition of the end of study

Abbreviations: AE = adverse event; App = application; eDiary = electronic diary; EoS = end of study; LAR = legally acceptable representative; MMRVNS = investigational measles, mumps, rubella, and varicella vaccine; MMRV = comparator measles, mumps, rubella, and varicella vaccine; SAE = serious adverse event

Notes:

The double-line border following Visit 3 (Day 43) indicates the analyses which will be performed on all data obtained up to Visit 3 (Day 43).

• is used to indicate a study procedure that requires documentation in the individual electronic case report form (eCRF).

o is used to indicate a study procedure that does not require documentation in the individual eCRF.

[†] Visit 2 (Day 15) may be conducted in-person or virtually.

*Blood sampling before the study interventions.

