Systemic reactions (i.e., fever, drowsiness, loss of appetite)	Systemic adverse reactions to vaccination are common but generally mild to moderate in severity.	Solicited systemic events will be collected for each participant. Medical advice as per the standard of care will be available.					
Systemic reactions such as measles/rubella-like rash, varicella-like rash	Mild disease-like rashes may occur after administration of the study vaccine (see the IB for details).	Measles/rubella-like rash, varicella- like rash and other rash will be collected as solicited systemic events.					
Hypersensitivity reactions (including anaphylaxis)	Acute allergic reactions such as an anaphylactic event may occur with any vaccine administration shortly after the intervention. These are serious, but rare occurrences.	Participants with known hypersensitivity to any component of the vaccines will be excluded from enrollment. All participants will remain under observation for at least 30 minutes after vaccination.					
Study Procedures – Blood Sampling							
Pain and bruising	Pain or bruising at the site where blood is drawn.	A topical analgesic may be applied to the site where blood will be taken.					
Syncope	Syncope (fainting) can occur following or even before any blood draw as a psychogenic response to the needle injection.	All participants will remain under observation at the clinical center for at least 30 minutes after vaccination.					

Table 5 Risk Assessment and Risk Mitigation Strategy

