8.3 Adverse Events, Serious Adverse Events, and Other Safety Reporting

8.3.1 Time Period and Frequency for Collecting AE and SAEs and Other Safety Information

The definitions of an AE or SAE are provided in Appendix 3.

Collection of AEs starts on the day of the study intervention (Day 1) up to Day 43 unless the AE leads to study discontinuation. Collection of SAEs starts the day of the study intervention (Day 1) and up to study end (Day 181) unless the SAE leads to study discontinuation. The frequency for collection of AEs and SAEs is shown in the SoA (Section 1.3).

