10.3.1.1 Events Meeting the AE Definition

- Significant or unexpected worsening or exacerbation of the condition/indication under study.
- Exacerbation of a chronic or intermittent preexisting condition including either an increase in frequency and/or intensity of the condition.
- New conditions detected or diagnosed after administration of the study intervention even though they may have been present before study start.
- Signs, symptoms, or the clinical sequelae of a suspected drug, disease or other interaction.
- Signs, symptoms, or the clinical sequelae of a suspected overdose of either the study intervention or a concurrent medication.
- Signs or symptoms temporally associated with administration of the study intervention.
- Signs, symptoms that require medical attention (e.g., hospital stays, physician visits and emergency room visits)
- Significant failure of an expected pharmacologic or biological action.
- Pre- or post- intervention events that occur as a result of protocol-mandated procedures (i.e., invasive procedures, modification of participant's previous therapeutic regimen).
- Clinically significant abnormal laboratory findings or other abnormal assessments that are present at baseline and significantly worsen following the start of the study will also be reported as AEs or SAEs.
- AEs to be recorded as solicited AEs are described in the Section 10.3.3.
- All other AEs will be recorded as UNSOLICITED AEs.
- The signs, symptoms, and/or clinical sequelae resulting from lack of efficacy will be reported as AE or SAE if they fulfill the definition of an AE or SAE.

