#### 16. SAFETY OUTCOMES

All outputs for safety outcomes will be based on the ES.

There will be no statistical comparisons between the study interventions for safety data.

Secondary Safety Endpoints:

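### SAP Section 11 files harms of the pre-dose blood draw as Medical History, against the protocol's AE definition and its consent-onward SAE row; separately, the Day 43 AE limit can fall before the Visit 3 draw

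*SAP*

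**What the plan says.** **SAP, recording rule.** Under Section 11, medical occurrences that start before dosing but "after obtaining informed consent will be recorded on the Medical History section of the eCRF, not the AE section". Medical History is then summarized on the Enrolled Set by system organ class and preferred term, and listed. Section 3.3, which sets out departures from the protocol, does not mention this rule.

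**Protocol, what counts and from when.**
- Section 10.3.1.1 includes among AEs: "Pre- or post- intervention events that occur as a result of protocol-mandated procedures".
- Section 1.3, Table 3, has a row headed "Recording of SAEs related to study participation, or to a concurrent GSK medication/vaccine". Its note reads: "The collection and reporting periods start once the participants' parent(s)/LAR(s) informed consent is obtained".
- Section 8.3.1 gives the general rule. AE and SAE collection both start on the day of dosing (Day 1); AEs run to Day 43 and SAEs to Day 181.
- Section 10.3.1.2 says that signs and symptoms already present before the first dose are not AEs, and places them in the medical history part of the eCRF.

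**Protocol, the blood draws.** Section 1.3 puts the Visit 1 sample before the study intervention, and Table 4 allows Visit 3 from 35 to 56 days after Visit 1. Section 2.3.1, Table 5, lists pain, bruising and fainting as risks of sampling: "Syncope (fainting) can occur following or even before any blood draw".

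**SAP, safety outputs.** Section 16 states: "All outputs for safety outcomes will be based on the ES". Section 16.1 limits every AE summary to treatment-emergent events, meaning onset at or after dosing. Section 16.1.4 tabulates post-dose SAEs and gives SAEs their own eCRF page. Section 16.1.3 and Appendix 2 contain handling rules for AE records with onset before vaccination.

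**The concern.** Apart from vaccination, the blood draw is the one invasive procedure that the study imposes on healthy 4- to 6-year-olds, and half of the planned draws come before the dose. If a child faints and is hurt at that draw, the study caused the event. The protocol's AE definition treats it as an AE, and if it is serious the Table 3 row collects it from consent. The SAP rule files it beside pre-existing conditions.

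The place of recording matters because the two data streams carry different information. For unsolicited AEs and SAEs the protocol requires intensity (10.3.6), causality (10.3.7) and outcome (10.3.9), and it names a protocol-required procedure as a possible contributing factor for an SAE. For Medical History the SAP describes only coded terms and a listing. A reader of the AE and SAE tables could not tell whether the pre-dose draw had harmed anyone.

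**Working it through.** There is no figure in the plan to reproduce. The check traces events through the rules, followed by two counts.

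**1. Four kinds of event**

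- *Non-serious, caused by the Visit 1 draw, onset before the dose.* It is an AE under Protocol 10.3.1.1. It is Medical History under SAP 11, and arguably under Protocol 10.3.1.2 as well. SAP 16.1 keeps it out of every AE summary. It is visible in the Medical History table and listing.
- *Serious, caused by the Visit 1 draw, onset before the dose.* It is collected from consent under the Table 3 row and belongs on the separate SAE page under SAP 16.1.4. SAP 11 nevertheless says Medical History. Even if it is recorded as an SAE, the treatment-emergent restriction and the post-dose wording of 16.1.4 keep it out of the SAE tables.
- *Serious, onset before Day 1, unrelated to study participation or to a concurrent GSK product.* Neither Table 3 nor Protocol 8.3.1 collects it as an SAE, so SAP 11 conflicts with neither collection rule here.
- *Any event with onset after the dose, including a late effect of the draw.* It is treatment-emergent and unaffected.

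The conflict is therefore confined to the first two kinds.

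**2. Children drawn but not dosed**

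SAP 5.2 counts a child with a pre-dose blood draw as enrolled, whether or not a dose follows. SAP 5.3 requires a dose for the Exposed Set. A child hurt at the draw and then not vaccinated is in the Enrolled Set only, so the Exposed Set rule in SAP 16 is a second, independent reason for absence from the safety tables.

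**3. Draws concerned**

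Planned enrollment is about 800 (Protocol 9.5), with two draws each (Protocol 8.1.1):
- total draws: 800 × 2 = 1,600
- pre-dose draws: 800 × 1 = 800, or half.

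This is the number of opportunities, not of events. Only events that start between the draw and the dose are affected, and the documents give no rate for them.

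**4. The Visit 3 draw**

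SAP 6.1 defines Study Day as the date difference plus 1:
- window: 35 + 1 = Day 36 to 56 + 1 = Day 57
- length: 57 − 36 + 1 = 22 days
- days after the Day 43 limit: 57 − 44 + 1 = 14 of the 22.

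A non-serious event caused by a draw on Days 44 to 57 lies outside the collection period in Protocol 8.3.1. SAEs are unaffected, because they are collected to Day 181.

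**The case against.** The strongest reply is that SAP 11 largely repeats Protocol 10.3.1.2, so the SAP is following the protocol. That is partly right: the tension between 10.3.1.1 and 10.3.1.2 lies inside the protocol, and editing the SAP alone would not remove it. But 10.3.1.1 is the specific text on events caused by study procedures, and SAP 11 carries no such exception.

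Three stronger readings are tempting, and the documents do not support them.

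- *That the protocol collects all SAEs from consent.* Only those related to study participation or to a concurrent GSK product start then; Section 8.3.1 starts the rest on Day 1. Consent, draw and dose all belong to Visit 1, so the Day 1 rule, stated as a day, can cover a same-day pre-dose event. The starting points clearly separate when consent falls on an earlier day, for example if Visit 1 is rescheduled (Section 8.2.1.2).
- *That these events disappear from the safety record.* They remain in the Enrolled Set Medical History table and listing, and SAP Section 6 lists all collected data for the Enrolled Set by default. SAP 16.1.3, 16.1.4 and Appendix 2 also foresee pre-vaccination AE records and a separate SAE page. Those provisions show that SAP 11 is not the SAP's only word on the matter, which is itself an inconsistency.
- *That a serious event would miss its 24-hour report.* That duty rests on Protocol 8.3.3 and 10.3.10, and a SAP sentence on Medical History does not override it.

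On Visit 3, 14 of 22 counts calendar days, not children. The protocol aims for 42 days whenever possible, so most visits may fall close to Day 43. The gap remains for those that fall later.

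**Conclusion.** The point holds as a recording and reporting inconsistency that should be fixed. Events caused by the pre-dose draw that start before dosing are AEs under one protocol section, Medical History under another and under SAP 11, and absent from every AE and SAE table under SAP 16 and 16.1. The separate Visit 3 gap is real for non-serious events only.

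The size is limited. About 800 planned pre-dose draws are exposed to the conflicting rules, assuming that enrollment meets its target and every child is sampled. No event count can be given, because the documents state no rate. Every safety endpoint in Protocol Table 6 is defined after the dose, so correcting the pre-dose rule changes no endpoint percentage and no treatment-emergent table. What is at stake is whether the harms of a study procedure in healthy children are assessed and reported as such.

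**What to change.** 1. **SAP 11.** Except two groups from the Medical History rule: AEs caused by a protocol-mandated procedure, and SAEs related to study participation or to a concurrent GSK product. Align the text with SAP 16.1.3, 16.1.4 and Appendix 2, which already provide for such records.
2. **Protocol 1.3 (Table 3), 8.3.1, 10.3.1.1 and 10.3.1.2.** Reconcile these sections on when AE and SAE collection starts and where a pre-dose procedure-related event is recorded.
3. **SAP 16.1.4.** Add one listing on the Enrolled Set of pre-dose procedure-related AEs and study-participation-related SAEs. State it as an exception to the Exposed Set rule in Section 16 and keep it apart from the treatment-emergent tables. Without it, a corrected Section 11 would still leave these events in no AE or SAE summary.
4. **Protocol 8.3.1 and Table 4.** Reconcile the Day 43 limit for non-serious AEs with the Visit 3 window, so that events related to that draw are recorded even when the visit falls after Day 43.

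The cost is wording in two documents, an update to the eCRF completion guidance and one listing. No visit, sample or extra staff is needed.

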## 12. PRIOR, CONCOMITANT AND CO-ADMINISTERED VACCINATIONS

Prior, concomitant and co-administered vaccination will be coded with the current version of the World Health Organization Drug Dictionary.

- Prior vaccinations are vaccinations per protocol given to participants prior to the dosing of study intervention and are recorded on the eCRF.
- Concomitant vaccinations are defined as any vaccine that the participant is receiving as of the time of enrolment

Analysis Plan Page 37 of 57

or receives during the study (other than study interventions) as recorded on the "Concomitant Vaccination" page of the eCRF.

#### 13. MEDICATIONS

The percentage of participants who started medications after study intervention will be presented by study intervention for the ES. Medications will be presented by Anatomical Therapeutic Chemical (ATC) classification and preferred drug name and by study intervention.

See APPENDIX 2 for handling of partial dates for medications, in the case where it is not possible to define a medication as prior or concomitant, the medication will be classified by the worst case; i.e., concomitant.

- 'Prior' medications are medications which started prior to the dose of study intervention.
- 'Concomitant' medications are medications which started on or after the day of the administration of study intervention.

Further details are in Section 6.8 of the Protocol. Concomitant medications which started from Day 1 to Visit 3 blood sample will be presented in table summaries (Any, antipyretic action) and in listings for all medications.

#### 14. STUDY INTERVENTION EXPOSURE

Exposure to study intervention will be presented for the ES. The date and time of study intervention administration will be taken from the eCRF "Exposure-MMRVNS vaccine/ProQuad vaccine" form. For dosing instructions and route, refer to Table 8 of the Protocol.

Data will also be presented in listings.

Analysis Plan Page 38 of 57

#### 15. IMMUNOGENICITY OUTCOMES

### 15.1. Primary Immunogenicity

#### 15.1.1. Primary Immunogenicity Variable(s) & Derivation(s)

The primary objective is to evaluate the immune response to the MMRVNS vaccine (formulated with different potencies) and the MMRV vaccine (pooled group) in terms of GMC at Day 43 for antibodies to measles, mumps, rubella and varicella. For the derivation of GMC refer to section 6.6.

## 15.1.2. Intercurrent Event Handling and Data Imputation for Primary Immunogenicity Variable(s)

Missing data will not be replaced.

